
time point. All response observations, including information from subjects who do not complete all experimental sessions, will be included in the analyses. Similar mixed-model analyses will be performed on the primary pain outcome after adjustment for psychomimetic side effects (measured with the ARCI scale) to assess for effects of the study drug on pain independent of subjective responses. The proportion of subjects with a 30% pain reduction, a standard for effective pain reduction⁶⁰ will be compared between each of the doses with chi-square tests; we will also calculate the number needed to treat (NNT) for a 30% pain reduction rate. We will also conduct analyses to examine the association between pain and EC biomarkers, including AEA, 2-AG, FAAH, and MAGL expression. A 5% significance level will be used for all testing. The association of pain levels with HRV will use a linear mixed-effects model, adjusting for potential confounders as above. Within-subject correlation will be accounted for using subject-specific random intercepts and slopes.

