7.2 Aim 2 Measures and Analyses

Based on our existing data for PLWH SMS compliance, we anticipate that participants will respond to 80-90% of the daily text messages during IMPACT. To address the issue of missing data, we will incorporate questions that allow participants to indicate their pain and cannabis use for the prior day if they did not respond to the earlier message. For days that have completely missing data, we will treat the intermittently missing data as missing completely at random. However, this assumption will be checked in sensitivity analyses by comparing the outcomes of participants based on the amount of missing data. Study dropout will be examined separately using statistical methods in current use [Diggle, Heagerty, Liang, and Zeger, *Analysis of Longitudinal Data*, 2nd ed., Oxford University Press, 2013]: The relationship between CBD, THC, and the CBD/THC ratio during a cannabis exposure event to changes in pain before and after the event will be examined using longitudinal data methods – e.g., mixed-effects linear models, controlling for potential confounders including baseline pain, in addition to those listed under Aim 1. The total CBD and THC consumed during the exposure will be calculated using the SUI method, estimating total grams of cannabis consumed multiplied by the percentages of CBD and THC content. Subject-specific random intercepts will be included in the model in order to account for the within-subject correlation of the outcome. Exploratory analyses will examine if there are different effects of reported cannabis strain (Sativa, Indica), individual types (e.g., OG Kush, Sour Lemon, etc.), or mode (smoking, vaporizing, ingesting food product) on pre-post changes in NP. We will also conduct exploratory analyses to examine if there is an interaction between reported levels of THC (low, < 1%, medium, 1-6%, high, > 10%) and CBD (low, < 1%, medium, 1-6%, high, > 10%) on pain change after drug use. The association of daily measures of pain levels with HRV will use a linear mixed-effects model, adjusting for potential confounders. The within-subject correlation will be accounted for using subject-specific random intercepts. Longitudinal changes in HRV between the first and last week will be assessed with a linear model that includes cannabis use (light vs. heavy) and CBD/THC intake, as predictors. Regression analyses will also examine the association between HRV and self-report pain measures quantified at the baseline and final visits.

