For Aim 2, with 20% attrition over the 6 months of IMPACT we have $n= 80$ participants with 6 months (26 weeks) of data. We conservatively ignore the drop-out participants (who nonetheless contribute partial data). Assume, conservatively, that participants will use cannabis on average 2 times/week. This gives $n=80$ and $k=52$ observations/participant. If ICC is the intra-class, or within-participant correlation, the effective sample size (number of equivalent independent observations) is $n_{\text{eff}} = n/(ICC+(1-ICC)/k) \approx n/ICC$ [e.g., Killip, Mahfoud, Pearce, Ann Fam Med, 2004; 2:204-208.]. Assuming conservatively $\rho=0.5$ (or lower), we get $n_{\text{eff}} = 2n = 200$ [$n_{\text{eff}} = 160$]. We have 80% power to detect a (partial) correlation R between the individual predictors (Hypothesis 1: CBD, THC, and the CBD/THC ratio; Hypothesis 2: pain levels and HRV) and change in pain of $R = 0.218$ (or semi-partial $R^2 = 0.0475$), after adjusting for confounders. Calculations used G*Power.

For Aim 3, assuming $n = 80$ participants complete the 6-month follow-up, we have 80% power to detect an association between an individual predictor and response (e.g., total CBD and changes in neuropathic pain levels) of $R = 0.302$ (or semi-partial $R^2 = 0.092$), after adjusting for confounders. The calculations used G*Power.

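### Aim 2 mixed models have random intercepts but no random slopes or robust errors, so their tests exceed 5% if within-person slopes differ between participants

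*Combined protocol and SAP*

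**What the plan says.** Section 7.1 closes with the Aim 1 pain-HRV model: "Within-subject correlation will be accounted for using subject-specific random intercepts and slopes". It does not say which variable the slopes belong to. It also sets the test level: "A 5% significance level will be used for all testing".

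Section 7.2 describes two repeated-measures models on IMPACT data:

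- **Event-level model.** CBD, THC and their ratio are related to pain change around each use event. The method is offered as an example: "mixed-effects linear models, controlling for potential confounders including baseline pain, in addition to those listed under Aim 1". The random structure is then stated: "Subject-specific random intercepts will be included in the model in order to account for the within-subject correlation of the outcome".
- **Daily pain-HRV model.** "The association of daily measures of pain levels with HRV will use a linear mixed-effects model, adjusting for potential confounders". Its random structure is: "The within-subject correlation will be accounted for using subject-specific random intercepts".

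Section 7.2 names no random slope, robust standard error or residual correlation structure for either model, and gives no reason for differing from 7.1. Section 2.0 lists the association of dispensary cannabis with pain change as the Aim 2 primary outcome. Section 7.4 names both associations as Aim 2 hypotheses.

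**The concern.** A random intercept allows for people whose pain is generally higher or lower. It does not allow for people whose pain responds differently to CBD, THC or HRV. If responses differ, the average slope is known only as well as the number of participants permits, however many readings each one gives. An intercept-only model treats every reading as fresh evidence on that average, so its standard error keeps shrinking as readings accumulate.

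Aim 1 has at most 15 readings per person (3 sessions x 5 time points, Section 4.2). Aim 2 has 52 on the plan's figures, and possibly about 150 for daily data. The plan therefore names no slopes in the aim where leaving them out would matter more. At stake is the false-positive rate of the Aim 2 primary association and of the pain-HRV hypothesis.

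**Working it through.** **Inputs from the documents.** Section 7.4: 20% attrition of 100, so n = 80; 2 events a week over 26 weeks, so k = 52; ICC 0.5. Section 7.2: 80-90% response to daily texts, so 182 x 0.80 = 146 to 182 x 0.90 = 164 daily reports; k = 150 is used below (150/182 = 82%). Section 7.1: 5% level, taken as two-sided because sidedness is not stated.

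**Assumed.** Predictor and outcome are standardised, so within-person residual variance is 1 - 0.5 = 0.5. The predictor varies only within person. The true mean slope is zero. The between-person slope SD (tau) is not given anywhere, so a range from 0 to 0.20 is shown.

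**Step 1: the plan's own figure.** The effective sample size is 80/(0.5 + 0.5/52) = 157.0, or 80/0.5 = 160 by the plan's approximation. At 160, power for R = 0.218 is 0.802, and the R detectable at 80% power is 0.2175. The stated figure reproduces. It allows for an ICC and not for slope variation.

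**Step 2: standard error ratio.** The true variance of the estimated mean slope is tau²/n + (1 - ICC)/(nk). The intercept-only model reports about [(1 - ICC) + tau²]/(nk). The number of participants cancels:

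ratio of true to reported SE = sqrt{ [tau² + 0.5/k] / [(0.5 + tau²)/k] }

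actual rejection rate = 2 x [1 - Φ(1.96/ratio)]

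Example, tau = 0.10 and k = 52: (0.0100 + 0.00962)/(0.51/52) = 0.01962/0.00981 = 2.00. The square root is 1.41, 1.96/1.414 = 1.386, and the rejection rate is 17%.

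**Step 3: results.** Each cell gives the SE ratio, then the actual rejection rate.

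| tau | k = 24 | k = 52 | k = 150 |
|---|---|---|---|
| 0 | 1.00, 5% | 1.00, 5% | 1.00, 5% |
| 0.05 | 1.06, 6% | 1.12, 8% | 1.32, 14% |
| 0.10 | 1.20, 10% | 1.41, 17% | 1.98, 32% |
| 0.20 | 1.64, 23% | 2.19, 37% | 3.47, 57% |

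The k = 24 column is the upper end of light use in the Schema (4 a month x 6 months).

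**Step 4: simulation.** At n = 80 and ICC 0.5, an intercept-only analysis rejected 8 / 16 / 36% at k = 52 and 12 / 32 / 56% at k = 150 for tau = 0.05 / 0.10 / 0.20. A separate run scaled the slope SD by the residual SD (h = tau/sqrt(0.5), so tau = 0.10 is h = 0.141). Fitted intercept-only mixed models at k = 52 rejected 9.5% at h = 0.1 and 30% at h = 0.2 (200 replicates each), against 11.0% and 25.5% from the formula.

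**Step 5: predictor partly between people.** With half of the predictor's variance between participants, simulated rejection at k = 52 was 8.0% at h = 0.1 and 17.8% at h = 0.2. With a purely within-person predictor it was 11.9% and 26.8%.

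**Step 6: after repair.** Cluster-robust tests rejected 4.3-5.5% at k = 52 and 4.5-7.7% at k = 150. A test on per-person slopes rejected 4.3-5.6%. Fitted random-slope models gave 3% and 8% in 200 replicates each (Monte Carlo error about 1.5 points).

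**The case against.** The strongest reply is that the documents give no evidence that slopes vary, and with no variation the stated models are correct. That stands: the excess is conditional. But the plan itself looks for varying effects. Section 7.3 tests whether CBD and THC effects differ between light and heavy users, and 7.2 explores differences by strain, product and mode. Zero variation is not a safe default.

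Other points limit the scope:

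- **HRV frequency is not stated.** The k = 150 column applies to pain-HRV only if HRV is paired with each daily pain report.
- **Light users have few events.** One to four uses a month gives about 6 to 24 events over six months, where the excess is smaller. Unequal counts can also work the other way. If, as an assumption, 40 people had 15 events and 40 had 89 (mean still 52), the heavier users would supply 3560/4160 = 86% of readings, and the rate at tau = 0.10 would rise from 17% to about 22%. This applies to the event model, because daily texts go to everyone.
- **Some predictors may barely vary within person.** Section 7.2 allows that many participants may use one or two products with a single CBD/THC ratio. That reduces the excess and makes a ratio slope hard to estimate.
- **The event model is introduced as an example.** That covers the type of model; the random-intercept sentence after it is a firm statement.

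A reader might infer that 7.1 already gives CBD and THC random slopes. It does not: its dose model has a subject random effect, and the slopes sentence follows the pain-HRV model without naming a variable. A reader might also infer that the 7.1-7.2 mismatch concerns the Aim 2 primary outcome. Section 2.0 lists HRV under Aim 1 only, and for the event-level model there is no mismatch with 7.1. The argument there rests on the statistics alone.

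**Conclusion.** The point holds as a conditional weakness that should be fixed because the repair is cheap. As specified, both Aim 2 models give tests that are too liberal whenever the within-person slope differs between participants. At the plan's 52 events per person the actual level is about 8 / 17 / 37% for an assumed slope SD of 0.05 / 0.10 / 0.20, and 5% at zero. At 150 readings it is about 14 / 32 / 57%, if HRV accompanies each daily pain report. These figures rest on a purely within-person predictor, ICC 0.5, equal counts and an assumed slope SD.

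The stronger reading, that the Aim 2 p-values are wrong or inflated several-fold, is not supported. The documents give no slope variance, and at the smallest non-zero value the excess at 52 events is modest. Nor does the ICC adjustment in Section 7.4 protect the test: it enters the sample-size calculation, not the standard error in the analysis.

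**What to change.** In Section 7.2, for both Aim 2 models, do one of the following:

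- report participant-level cluster-robust standard errors (about 80 clusters); or
- add a participant-specific random slope for the tested predictor, naming it: HRV in the pain-HRV model; CBD, THC or the ratio in the event model where it varies within person. If the slope variance does not converge, fall back to cluster-robust errors.

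Robust errors correct the standard error but leave the estimate weighted towards people with more readings; random slopes also even out that weighting. Section 7.1 should name the variable to which its slopes belong.

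The cost is a sentence or two of text, with no new data or participants. Intervals will be somewhat wider if slopes vary, and the ratio slope may not converge. The effect on power should not be judged by setting a detectable standardised slope against the stated R = 0.218, because a within-person slope and a partial correlation are different quantities.

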HIV-associated neuropathic pain (HIV-NP) affects a significant proportion of people living with HIV (PLWH) and has a major impact on everyday functioning and quality of life in this population. Over the past decade a growing number of preclinical studies and clinical trials have indicated that cannabis administration and manipulation of the endocannabinoid (EC) system may have therapeutic utility in addressing HIV-NP. EC CB2 receptor activation and inhibition of the EC deactivation enzymes fatty acid amide hydrolase (FAAH) and monoacylglycerol lipase (MAGL) have been shown to decrease pain in rodent models of HIV-NP, while acute exposure to cannabis reduces self-reported pain in PLWH with neuropathy. However, little work has been conducted to elucidate the effects of the two primary cannabinoids (delta-9-tetrahydrocannabinol, THC and cannabidiol, CBD) on the EC system or to assess EC function in PLWH. The objective of this application is to address these fundamental gaps in our knowledge by: 1) examining the acute effect of administering NIDA-prepared THC/CBD products on HIV-NP; 2) utilizing mHealth text messaging to monitor daily real-world self-administered cannabis effects on pain; 3) assessing the relationship between cannabinoids and EC biomarkers, including ligands, enzymes, and receptor expression; and 4) conducting exploratory analyses to evaluate the effect of longitudinal cannabinoid use on changes in HIV-NP over time. We will examine the effect of low (0.01%), medium (one vial of 5.1%), and high dose (two vials of 5.1%) CBD-containing cannabis on NP, the EC system, and heart rate variability (as a proposed objective biological measure of pain) in 100 PLWH who use cannabis to treat neuropathic pain. We will subsequently employ a mobile phone text messaging system, the Individual Monitoring of Pain And Cannabis Taken (IMPACT), to track cannabis exposure, CBD and THC consumption, and pain over a period of 6 months in these same PLWH participants. IMPACT will be used to quantify the real-time effects of acute CBD/THC exposure on pain before and after cannabis self-administration, the real-time relationship between self-reported pain and changes in HRV, and to assess any longitudinal changes in NP, HIV clinical outcomes (viral load, CD4) and cognition during the 6-month period. This plan allows us to acquire data and compare the effects of cannabis product obtained from NIDA and self-administered cannabis obtained from local medicinal dispensaries. The overarching hypothesis is that CBD exposure and a higher CBD/THC ratio will exert beneficial effects both in the laboratory and during the observational study, including increasing EC biomarkers and reducing NP. In summary, this approach will advance our understanding about several key issues, including the interaction between cannabis constituents, the EC system and pain, the biological mechanisms that underlie these effects (EC enzymes, receptor), and the longer-term effects of cannabis use on health-related outcomes in HIV, including predictors of mortality (HRV, CD4, viral load) and neurocognition.

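### HRV change during IMPACT is assessed from the first and last weeks only; a mixed model on all recorded HRV, with leavers included, would be a cheap improvement

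*Combined protocol and SAP*

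**What the plan says.** In Section 7.2 (Aim 2), "Longitudinal changes in HRV between the first and last week will be assessed with a linear model". The predictors named for it are light or heavy use and the intake of CBD and THC. Just before this, the section treats a different HRV question differently: "The association of daily measures of pain levels with HRV will use a linear mixed-effects model", and "The within-subject correlation will be accounted for using subject-specific random intercepts". The opening summary says that IMPACT will also quantify "the real-time relationship between self-reported pain and changes in HRV".

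On follow-up, Section 7.4 plans "with 20% attrition over the 6 months of IMPACT", which leaves 80 of 100 participants with 26 weeks of data, and notes that those who leave still supply partial data. Section 7.2 says that dropout will be examined separately by current longitudinal methods, citing a textbook, and that outcomes will be compared by amount of missing data. It does not tie either step to the HRV-change analysis.

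No section states how often HRV is recorded during IMPACT. Section 4.3 describes the text messaging without mentioning HRV, and Section 4.2 schedules HRV for the laboratory sessions only.

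**The concern.** A first-to-last-week change uses two of 26 weeks. If HRV is recorded in between, as a mixed model of daily pain and HRV implies, those values do not inform the estimate of change. If the model is fitted to one change score per person, anyone without a last-week value drops out of it, although the plan itself says that leavers contribute data.

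Two things are at stake for the question whether cannabinoid intake predicts HRV change. One is precision. The other is reliance on completers: a change-score analysis can be biased if leaving depends on earlier HRV, whereas a correctly specified likelihood model that includes those earlier values remains valid when data are missing at random. The same paragraph already plans a mixed model for the neighbouring HRV question, so the better method is close at hand.

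**Working it through.** **Inputs from the documents.** 100 participants, 20% attrition, 26 weeks, k = 52 observations per participant and ICC 0.5 (Section 7.4); 5% significance level (Section 7.1; two-sided assumed).

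**Inputs assumed, because the documents give none.** One HRV value per week; weekly error variance 1; AR(1) correlation ρ between weekly errors; a linear trend; between-person variance τ² of the true first-to-last-week change, in units of the weekly error variance.

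**1. The plan's own power figures.** n_eff = n/(ICC + (1 − ICC)/k) = 80/(0.5 + 0.5/52) = 157.0. The plan's approximation n/ICC gives 160. With f² = R²/(1 − R²), noncentrality f²n and 80% power, the F test of one coefficient gives a detectable R of 0.2175 at n = 160 (plan: 0.218 for Aim 2) and 0.3023 at n = 80 (plan: 0.302 for Aim 3). Both reproduce. Neither is stated for HRV change. An analysis with one change value per person at n = 80 corresponds to 0.302, not to 0.218.

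**2. Data used.** Weeks: 2/26 = 7.7% used, 24/26 = 92.3% not used. Participants without a last week: 100 × 0.20 = 20.

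**3. Precision among completers.** The variance of one person's estimated change is:

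- two end weeks: v_end = 2(1 − ρ^25);
- all 26 weeks: v_all = 25² × the generalised least squares variance of the slope. For ρ = 0, Σ(t − t̄)² = 26(26² − 1)/12 = 1462.5, so v_all = 625/1462.5 = 0.427.

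The ratio of standard errors is √[(τ² + v_all)/(τ² + v_end)]. With every completer observed for all weeks, it carries over to the coefficient of an exposure on change.

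| ρ | v_end | v_all | SE lower, τ² = 0 | τ² = 1 | τ² = 2 |
|---|---|---|---|---|---|
| 0 | 2.000 | 0.427 | 54% | 31% | 22% |
| 0.5 | 2.000 | 1.027 | 28% | 18% | 13% |
| 0.7 | 2.000 | 1.484 | 14% | 9% | 7% |
| 0.9 | 1.856 | 1.820 | 1% | 0.6% | 0.5% |

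For example, at ρ = 0.5 and τ² = 2: √(3.027/4.000) = 0.870, which is 13% lower.

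**4. Adding the leavers.** Let 20 exits be spread evenly over weeks 2 to 25, with random-intercept variance 1. At ρ = 0.5 and τ² = 1, the variance of the mean change is 3/80 = 0.0375 from end weeks in 80 completers, 0.0253 from a mixed model in the same 80, and 0.0232 once the leavers' partial series are added. The overall variance ratio is 0.0375/0.0232 = 1.62; the leavers account for a factor of 0.0253/0.0232 = 1.09. Over τ² from 0.5 to 2, the overall ratio is 1.84 to 2.93 at ρ = 0 and 1.46 to 1.78 at ρ = 0.5.

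**The case against.** The strongest objection is that the plan may be discarding nothing. No HRV schedule for IMPACT is given. In "The association of daily measures of pain levels with HRV" the word daily attaches to pain, and the 52 observations in Section 7.4 count cannabis-use occasions, not HRV recordings. The wording of the change analysis would also fit HRV recorded only in the two end weeks. This stands as a limit: a reader might infer that a full HRV series is in hand and thrown away, but the documents only imply repeated HRV. Any intermediate values also remain in use for the separate pain-HRV question.

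Second, a reader might infer an ordinary regression that certainly loses every leaver. The text does not say so. Section 7.1 itself refers to its mixed model as a linear model further on, the last week is not defined for someone who leaves, and a mixed model of two weeks would keep first-week values. The change-score reading is natural given the contrast with the adjacent sentences, but it is a reading.

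Third, the plan does examine dropout and compares outcomes by amount of missing data. That deserves credit, although neither step puts leavers into this model.

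Fourth, the all-weeks model has its own costs. Its slope equals the planned change only under a linear trend, and total intake is cut short for leavers. This stands, and the fix has to deal with it.

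Finally, HRV change is not among the Aim 2 or Aim 3 primary measures in Section 2.0, and no power is claimed for it.

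**Conclusion.** The point holds as a minor, cheap improvement to one supporting analysis. On the change-score reading, the planned model leaves out any HRV recorded between the end weeks and about 20 of 100 participants. The size is conditional. Among completers with weekly HRV and a linear trend, the standard error would be 13% to 28% lower at ρ = 0.5 (τ² from 2 down to 0) and about 1% lower or less at ρ = 0.9. The 54% figure needs independent weekly errors and no between-person variation in true change, so it is an upper end and not an expectation. If only the two end weeks are recorded, the gain from intermediate weeks is nil.

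A reader might go further and conclude that the HRV-change result will be biased. The documents contain nothing on whether leaving relates to HRV, pain or use, so bias is possible but not shown. Nor does the point touch the pain analyses.

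**What to change.** - **State the data.** Give the HRV recording schedule during IMPACT, and define the last week for participants who leave early.
- **Main analysis.** Fit a linear mixed model to all HRV values recorded during IMPACT, with time, exposure and time × exposure, participant random intercepts and random slopes for time, and leavers' data included. With time scaled so that one unit spans the first to the last week, the interaction is the exposure difference in change over that period.
- **Exposure.** Define it so that it is comparable for leavers: for example, the baseline light/heavy group and average weekly CBD and THC intake while observed, not the total. An average taken over the whole observed period still relates early HRV to later intake, so the result should be described as an association.
- **Sensitivity analysis.** Keep the first-versus-last-week contrast as a check for a non-linear trend.
- **If only the two end weeks are recorded.** Fit the same mixed model to those two weeks, so that leavers' first-week values are kept. With a single value per week, the random slope cannot be separated from residual error; an unstructured covariance for the two weeks serves instead.

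The cost is SAP wording and a little more analysis work, with no new visits, participants or measurements. The downside is reliance on a linear trend, which the retained contrast checks.

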2.0 STUDY DESIGN

Our objective is to assess 100 community-dwelling PLWH with neuropathic pain (PLWH-NP) who are recruited and tested at the HIV Neurobehavioral Research Program (HNRP)/Center for Medicinal Cannabis Research (CMCR) facilities located at the UCSD Medical Center. These participants will be enrolled in a study that consists of two stages: 1) administration of three different doses of vaporized cannabis obtained from NIDA (one dose per day on three separate days) that contain THC and varying concentrations of CBD, including: a) 2 vials of 0.01% CBD + 1.9% THC, b) 1 vial of 0.01% CBD + 1.9% THC and 1 vial of 5.1% CBD + 1.4% THC, and c) 2 vials of 5.1% CBD + 1.4% THC; 2) participation in a 6-month text message monitoring study, the Individual Monitoring of Pain and Cannabis Taken (IMPACT), where pain and cannabis use from local dispensaries is tracked. We will use a randomized crossover design where all participants receive each of the three cannabis doses at the HNRP and then are subsequently enrolled into IMPACT. We will recruit individuals who are currently using cannabis at least once a month to treat pain. The primary outcome measures of the study will examine: 1) the acute effects of NIDA-obtained cannabis on pain, EC levels, and the relationship with HRV (Aim 1); 2) the association between dispensary-obtained cannabis and changes in pain reported via IMPACT (Aim 2); 3) the effect of chronic THC and CBD exposure on longitudinal changes in pain, EC measures, and neurocognitive performance (Aim 3). Secondary and exploratory analyses will compare NIDA-obtained and dispensary-obtained cannabis effects on neuropathic pain and evaluate if there are different effects of reported cannabis strain (Sativa, Indica), specific cannabis products (e.g., OG Kush, Sour Lemon, etc.), or mode (smoking, vaporizing, ingesting food product) on pre-post drug exposure changes in pain

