
Comparison of NIDA-obtained and dispensary-obtained cannabis effects on NP. We will compare the effect of laboratory cannabis administration and IMPACT self-report data on changes in pain (both measured with NPRS) before and after drug exposure. We will assess pain change scores for the laboratory study and IMPACT measured as the difference between

baseline (before drug) and 60 and 120 minutes after drug, time points that correspond with pain reduction in our prior THC work⁶⁰. We will use the following analyses: 1) plot the distribution of the CBD/THC ratio (x-axis) against pain change (y-axis), calculate the slope of pain change scores for both the lab data and IMPACT, and determine if the slopes are similar or significantly different (a mixed effect model that will estimate changes in outcomes/slopes). 2) If the slopes are nonlinear, we will calculate the area under the curve (AUC) – a measure of total pain change – up to a CBD/THC ratio of 10 (our high CBD dose in the lab). 3) It is possible that our IMPACT data show that many participants only use one or two types of cannabis (e.g., with only a single CBD/THC ratio), thus it might be difficult to plot a CBD/THC ratio distribution. In that event, we will classify IMPACT cannabis use into 3 categories (low CBD/THC ratio, < 1; matched CBD/THC 1:1; high CBD/THC ratio, >1, and examine the correlation between the pain change in each category (averaged over the IMPACT study) with the pain change scores we observe for our low, medium, and high CBD laboratory doses. If our findings indicate a higher slope or greater AUC for NIDA cannabis vs. dispensary cannabis, this would suggest less efficacious pain relief from the local cannabis sources. In contrast, a strong correlation between CBD pain change scores for NIDA and dispensary product in one or more CBD/THC ratio categories would support a consistent finding for the effectiveness of different CBD amounts. In summary, either agreement or discrepancy between NIDA and dispensary data would be highly informative and would help guide future policy recommendations for cannabis-based pain treatment.

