7.4 Power Analyses

A recent study indicated a medium effect size (Cohen's $d = 0.46$) for CBD treatment that increased plasma AEA levels compared to an antipsychotic drug control condition²⁶. Preclinical models of neuropathic pain in mice demonstrate that FAAH inhibitors decrease hyperalgesia

and allodynia with large effect sizes (Cohen's $d = 4-5$)¹⁸. Our pilot HRV data indicate a medium to large effect size (Cohen's $d = 0.8$) for reduced RMSSD in PLWH with neuropathic pain compared to PLWH without neuropathy. We conducted power calculations with the G*POWER software⁹² comparing the area under the curve (AUC) of the change from baseline in pain levels between the three doses of cannabis. The actual analyses will have higher power, since they rely on a longitudinal mixed-effects model. With $n=100$ participants completing the cross-sectional baseline visits, and measured in a within-participant design, as described above, we have 80% power to detect an effect size Cohen's $f=0.180$. This Cohen's f corresponds to a range of group means for the three groups corresponding to a small-to-medium Cohen's $d = 0.382-0.441$. We have 0.61-0.76 power to detect such a pairwise difference as statistically significant in post-hoc analyses (e.g., with Bonferroni correction for post-hoc comparisons). If the completion rate at this stage is 95% (90%) of the initial enrollment of $n=100$, the detectable effect size is Cohen's $f=0.185$ (0.190). These correspond to a range of group means for the three groups corresponding to small-medium Cohen's $d = 0.403-0.465$.

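### The secondary NIDA-versus-dispensary slope comparison has no criterion for 'similar' and no inconclusive outcome, so its wording invites reading a non-significant test as agreement

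*Combined protocol and SAP*

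**What the plan says.** Section 7.2 of the combined protocol and SAP sets out three steps for comparing laboratory and dispensary cannabis. Step 1 plots pain change against the CBD/THC ratio, obtains a slope for each source, and will "determine if the slopes are similar or significantly different", using "a mixed effect model that will estimate changes in outcomes/slopes". The test level comes from section 7.1: "A 5% significance level will be used for all testing". Step 2 uses an area under the curve if the slopes are non-linear. Step 3 is a fallback using three ratio categories.

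Three sentences on interpretation follow. One begins "If our findings indicate a higher slope or greater AUC for NIDA cannabis vs. dispensary cannabis" and reads that result as poorer pain relief from local products. The next says that "a strong correlation between CBD pain change scores for NIDA and dispensary product in one or more CBD/THC ratio categories" would support consistency. The last says that "either agreement or discrepancy between NIDA and dispensary data would be highly informative" and links this to policy recommendations.

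Section 2.0 gives the status: "Secondary and exploratory analyses will compare NIDA-obtained and dispensary-obtained cannabis effects on neuropathic pain". Section 7.4 gives power for the Aim 1 dose contrast and for the Aim 2 and Aim 3 associations, but none for this slope comparison.

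**The concern.** Step 1 names two outcomes and gives a test for one of them. With nothing else defining similarity, a result that misses 5% significance has only one label left. Imprecise data make that label more likely, so the weaker the evidence, the more readily the two sources appear to agree. Agreement is then among the findings expected to inform policy. The trial could report that dispensary and NIDA products act alike on pain when it merely lacked the precision to tell them apart.

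**Working it through.** **Inputs from section 7.4.** n=100 in the laboratory; Cohen's f=0.180 at 80% power; low-to-high contrast d=0.382-0.441 SD; effective n of 160 for IMPACT (80 participants, ICC 0.5). Alpha is 0.05, taken as two-sided.

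**Inputs not in the documents (assumed).** A dispensary slope half the laboratory slope; an IMPACT standard error of 0.07-0.10 SD over the laboratory range; independent slope estimates; where stated, a between-session correlation of 0.5 or a true effect of 0.8 SD.

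**Reproducing the plan's figure.** For a repeated-measures F test of three doses with zero correlation between sessions, the non-centrality is 0.180² × 100 × 3 = 9.72 on 2 and 198 df. Power is 0.797, matching the stated 80%. A correlation of 0.5 would give 0.981, so zero is the value that the stated power implies. The d range follows as 0.180/0.471 = 0.382 (two doses alike, one apart) and 0.180/0.408 = 0.441 (evenly spaced doses).

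**Chance that a halved slope is non-significant.** Express each slope as the change from low to high laboratory dose, in SD units.

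- SE_lab = sqrt(2(1−ρ)/100), which is 0.141 at ρ=0 and 0.100 at ρ=0.5.
- SE_diff = sqrt(SE_lab² + SE_IMPACT²).
- z = 0.5d/SE_diff.
- P(non-significant) = 1 − [Φ(z−1.96) + Φ(−z−1.96)].

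Example: d=0.441, ρ=0, IMPACT slope exact. z = 0.2205/0.1414 = 1.56, so P = 0.66.

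| ρ | d | IMPACT slope exact | SE_IMPACT 0.07 | SE_IMPACT 0.10 |
|---|---|---|---|---|
| 0 | 0.441 | 66% | 71% | 75% |
| 0 | 0.382 | 73% | 77% | 80% |
| 0.5 | 0.441 | 40% | 56% | 66% |
| 0.5 | 0.382 | 52% | 65% | 73% |
| 0 | 0.8 | 19% | 28% | 36% |

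If the dispensary slope were zero, at ρ=0 and the planned d, the difference would still be non-significant in 12-23% of trials with an exact IMPACT slope, and in 20-40% with the assumed IMPACT error.

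**Second route, per unit of CBD/THC ratio.** Taking the vial percentages at face value and equal vial weights, the laboratory ratios are 0.01/1.9 = 0.005, 5.11/3.3 = 1.55 and 5.1/1.4 = 3.64. The dispensary slope is given the plan's effective n of 160, with the SD of the dispensary ratio assumed to lie between 0.75 and 3. At ρ=0, power to detect a halved slope is 0.08-0.25, or 0.27-0.35 with the dispensary slope exact. So 65-92% of such trials would be non-significant. This range is wider than the table's because the spread of dispensary ratios is unknown.

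**Precision.** At ρ=0 with an exact IMPACT slope, the 95% CI half-width for the difference is 1.96 × 0.141 = 0.277 SD. Half the larger planned effect is 0.441/2 = 0.22 SD.

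**The case against.** A reader might infer that the plan declares a non-significant slope test to be agreement. It does not say so. Its only explicit criterion for consistency is a strong correlation, which belongs to the step 3 categories, and the closing sentence covers all three steps without defining agreement. That stands: the reading is invited by the two-way wording and the missing criterion, not stated. The correlation rule does not fill the gap, because it has no cut-off and does not concern the step 1 slopes.

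A reader might also infer that most trials of this size would miss a halved slope whatever the circumstances. The documents do not support that. The 0.382-0.441 SD is a detectable effect, not an expected one. The zero correlation is inferred from the stated power, and section 7.4 says the actual mixed model will have more power. At ρ=0.5 with an exact IMPACT slope the miss rate is about even or below, and at 0.8 SD it is 19-36%. The same participants supply both slopes; with equal standard errors and a laboratory slope at 80% power, a correlation of 0.75 between the two estimates would raise power to 0.51. The IMPACT standard error has no source in the documents.

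Finally, the plan already estimates the slopes, and the comparison is secondary or exploratory. Both points stand. They narrow what is missing to an interval for the difference, a criterion for similarity and a third outcome. They do not remove the need, because the plan itself gives the result a policy use.

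**Conclusion.** The concern holds as a gap in the decision rule of a secondary or exploratory analysis. 'Similar' has no criterion, no inconclusive outcome exists, and nothing stops a non-significant test being reported as agreement.

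The size is conditional. At the effect the plan is powered to detect and the zero correlation its power figure implies, about two thirds to three quarters of trials would fail to separate a halved dispensary slope from the laboratory slope even without IMPACT error. The proportion rises with IMPACT error and falls with higher between-session correlation, larger true effects or strongly correlated slope estimates. The gap itself remains under all these conditions. Nothing here bears on the validity of the primary analyses of Aims 1 to 3.

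**What to change.** Amend step 1 in section 7.2 before any data for this comparison are analysed:

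1. Report the difference between the two slopes from the planned mixed model, with its 95% CI.
2. State that a non-significant difference is not evidence of agreement.
3. Conclude 'different' if the CI excludes zero, 'similar' if it lies wholly within a margin, and 'inconclusive' otherwise. State which label takes precedence when a CI excludes zero and also lies within the margin.
4. Set the margin as a number on the NPRS-change scale, over a stated ratio range. Do not derive it from the laboratory slope estimated in this trial, because it would then not be fixed in advance.
5. First reconcile the high laboratory CBD/THC ratio: section 7.2 puts it at 10, while the vial percentages in section 4.1 give 5.1/1.4 = 3.64. The range over which slopes are compared depends on it.

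The cost is SAP wording, with no new data or visits. The downside is that 'inconclusive' becomes a likely result. With a half-width of 0.277 SD, a margin equivalent to 0.22 SD could never be met, so the margin should be checked against the expected precision when it is chosen, and the likely outcome stated openly.
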